**NOTES:**

- Additional parameters may be included as required.

**Table 5 Derived Urine Pharmacokinetic Parameters**

Parameter	Parameter Description
Ae total	Total unchanged drug (total amount of drug excreted in urine), calculated by adding all the fractions of drug collected over all the allotted time intervals
Ae(t1-t2)	Amount of drug excreted in urine in a time intervals for predose, 0 to 6, 6 to 12, 12 to 24, or 24 to 36, and 36 to 48 hours after dosing for subjects with renal impairment; and predose, 0 to 2 hours, 2 to 4 hours, 4 to 6 hours, 6 to 8 hours, 8 to 12 hours, 12 to 24 hours, 24 to 36 hours, and 36 to 48 hours for subjects with normal renal function
AUC(0-t)	Area under the urine concentration-time curve over t hours where t = 12, 24, and 48 hours. The AUC(0-t) will be calculated by the linear trapezoidal rule based on the urine concentration data from each collection interval versus the corresponding urine collection interval.
fe%	Percentage of the given dose of drug excreted in urine, calculated as: $fe\% = (Ae\ total/Dose) \times 100$
CLr	Renal clearance of drug, calculated as: $CLr = Ae\ total/AUC(0-t)$

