### 2.2. Study Objective(s) and Endpoint(s)

Objectives	Endpoints
Primary Objectives	Primary Endpoints

 
To compare the PK of gepotidacin administered as a 750 mg IV dose in normal healthy subjects compared with subjects with mild, moderate, and severe renal impairment, and with subjects with ESRD.
 
	
 
Plasma primary PK endpoints include AUC(0-∞) and Cmax of gepotidacin, as data permit
 
Urine primary PK end points include Ae total, AUC(t0-t1), fe%, and CLr of gepotidacin, as data permit
 
Dialysate primary PK end points include AUC(t0-t1), CLD, and Frem%(0-4), of gepotidacin, as data permit
 

Secondary Objectives	Secondary Endpoints

 
To assess the safety and tolerability of gepotidacin administered as a 750-mg IV dose in normal healthy subjects compared with subjects with mild, moderate, severe renal impairment, and with subjects with ESRD
 
	
 
12-lead safety electrocardiogram readings, change from baseline in vital sign measurements (blood pressure and heart rate), monitoring of adverse events, toxicity grading of clinical laboratory test results, and physical examinations
 

 
To evaluate the secondary PK parameters of gepotidacin administered as a 750-mg IV dose in normal healthy subjects compared with subjects with mild, moderate, and severe renal impairment, and with subjects with ESRD
 
	
 
Plasma PK endpoints include AUC(0-t), CL, λz, t1/2, Tmax, Vss, and Vz, as data permit
 
Urine PK endpoint includes Ae(t1-t2) and AUC(0-t) as data permit
 
Dialysate PK endpoints include Arem(0-1), Arem(1-2), Arem(2-3), Arem(3-4), and Arem(0-4), as data permit
 

Exploratory Objectives	Exploratory Endpoints

 
To evaluate the saliva pharmacokinetics of gepotidacin (subjects in Part 1 only).
 
	
 
Primary saliva PK endpoints include AUC(0-∞) and Cmax of gepotidacin, as data permit
 
Secondary saliva PK endpoints include AUC(0-t), CL, λz, t1/2, Tmax, Vss, Vz, RAUC(0-t) and RAUC(0-∞) as data permit
 

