9.11.6. Pharmacokinetic Tables

Pharmacokinetic : Tables					
No.	Population	IDSL / TST ID / Example Shell	Title	Programming Notes	Deliverable [Priority]
PK Concentration Data					
3.1	PK	PK01	Summary of Gepotidacin Plasma Pharmacokinetic Concentration-Time Data (units) by Group	Blood samples for PK analysis will be collected at 1 predose time point and 0.25, 0.5, 1.0, 1.5, 2.0, 2.5, 3.0, 4.0, 6.0, 8.0, 12.0, 24 ,36 and 48 hours after dosing. If mean is below the level of quantification, report the mean value as NQ.	SAC [1]
3.2	PK	PK01	Summary of Gepotidacin Urine Concentrations (units)	Urine collection intervals for subjects with normal renal function (Group A and Group D) include 0 (pre-dose), 0 to 2 hours, 2 to 4 hours, 4 to 6 hours, 6 to 8 hours, 8 to 12 hours, 12 to 24 hours, 24 to 36 hours, and 36 to 48 hours. Urine collection intervals for subjects with renal impairment (Group B, Group C, and Group E) include 0 hour (pre-dose), 0 to 6 hours, 6 to 12 hours, 12 to 24 hours, 24 to 36, and 36 to 48 hours. If mean is below the level of quantification, report the mean value as NQ.	SAC[1]

Pharmacokinetic : Tables					
No.	Population	IDSL / TST ID / Example Shell	Title	Programming Notes	Deliverable [Priority]
3.3	PK	PK01	Summary of Gepotidacin Saliva Concentrations (units) by Renal Function	Blood samples for PK analysis will be collected at 1 predose time point and 0.25, 0.5, 1.0, 1.5, 2.0, 2.5, 3.0, 4.0, 6.0, 8.0, 12.0, 24 ,36 and 48 hours after dosing.If mean is below the level of quantification, report the mean value as NQ. Part 1 subjects only.	SAC [1]
3.4	PK	PK01	Summary of Gepotidacin Dialysate Concentrations (units)	Blood samples for PK analysis will be collected at 1 predose time point and 0.25, 0.5, 1.0, 1.5, 2.0, 2.5, 3.0, 4.0, 6.0, 8.0, 12.0, 24 ,36 and 48 hours after dosing. If mean is below the level of quantification, report the mean value as NQ. Part 2 subjects only. Part 2 subjects in Group F only	SAC[1]
3.5	PK	PK01	Summary of Gepotidacin Dialyzer Plasma Concentration (units)	Blood samples for PK analysis will be collected at 1 predose time point and 0.25, 0.5, 1.0, 1.5, 2.0, 2.5, 3.0, 4.0, 6.0, 8.0, 12.0, 24 ,36 and 48 hours after dosing. If mean is below the level of quantification, report the mean value as NQ. Part 2 subjects in Group F only	SAC[1]

Pharmacokinetic : Tables					
No.	Population	IDSL / TST ID / Example Shell	Title	Programming Notes	Deliverable [Priority]
PK Parameters Tables					

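### Urine AUC is a trapezoid over five collection intervals to 12 h in normal subjects but two in impaired subjects, so the descriptive comparison carries a collection-grid artefact

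*SAP*

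**What the plan says.** SAP Table 5 defines the parameter as "Area under the urine concentration-time curve over t hours where t = 12, 24, and 48 hours" and gives the rule as a linear trapezoid, "based on the urine concentration data from each collection interval versus the corresponding urine collection interval". Each interval supplies one concentration.

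The same table gives two collection schemes. Normal subjects collect at "predose, 0 to 2 hours, 2 to 4 hours, 4 to 6 hours, 6 to 8 hours, 8 to 12 hours", then 12-24, 24-36 and 36-48 h. Impaired subjects collect at "predose, 0 to 6, 6 to 12, 12 to 24, or 24 to 36, and 36 to 48 hours after dosing". The programming notes in SAP 9.11.6 confirm which groups use the coarse scheme: "Urine collection intervals for subjects with renal impairment (Group B, Group C, and Group E) include 0 hour (pre-dose), 0 to 6 hours". The schemes coincide only after 12 h.

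Table 5 does not say whether a concentration sits at the start, middle or end of its interval. The midpoint appears only as a plotting note for the urine concentration figures in SAP 9.11.7.

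SAP 2.2 lists this AUC as a secondary endpoint: "Urine PK endpoint includes Ae(t1-t2) and AUC(0-t) as data permit". The protocol's objectives and endpoints list no urine AUC, although SAP 2.1 reports no change from the protocol's planned analysis. SAP Table 3.7 summarises AUC(0-12), AUC(0-24) and AUC(0-48) for normal and impaired subjects by renal function.

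**The concern.** A trapezoid through interval-average concentrations depends on the interval widths. A 0-6 h collection averages the early peak into one value and delays the first positive point on the curve, so the area falls. Every normal subject has the fine grid and every subject in Groups B, C and E has the coarse one. Grid and renal function are therefore completely confounded in the normal-versus-impaired contrast.

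Lower urine concentrations are also a plausible effect of impairment. A reader of Table 3.7 could not tell how much of a lower urine AUC comes from the kidney and how much from the collection schedule. Comparisons among B, C and E share one grid and have no grid difference.

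**Working it through.** The documents give no figure for urine AUC or its error, so there is nothing to reproduce. The check puts one excretion curve through both grids.

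**Inputs.** The dose is 750 mg over 2 h (protocol 4.2). The documents give no half-life, so CL and V are assumptions anchored on the protocol where possible. Protocol Table 1 holds model predictions; its AUC(0-t) is treated here as total AUC.
- Normal: CL = 750/17.5 = 42.9 L/h. From Cmax 5.65 = (375/CL)(1 − e^(−2k)), k = 0.519/h, half-life 1.34 h, V = 82.6 L.
- Severe: CL = 750/28.9 = 26.0 L/h. With Cmax 7.93, k = 0.398/h, half-life 1.74 h, V = 65.2 L.
- Others: CL 43 L/h (protocol Appendix 11) or 750/25.8 ≈ 29 L/h (Table 1, moderate); V = 1.30 × 70 = 91 L (reading the Appendix 11 volume as L/kg and assuming 70 kg); and V = 150 L as a pure assumption.
- Constant urine flow and zero predose urine concentration (assumed).

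**Formulae.** Each interval concentration is the interval's share of the true AUC(0-12) divided by its length. Let P1 to P5 be the shares (%) in 0-2, 2-4, 4-6, 6-8 and 8-12 h, and Q1, Q2 those in 0-6 and 6-12 h. The linear trapezoid then reduces to:
- Concentration at interval end: normal P1 + P2 + P3 + 1.5·P4 + 0.5·P5; impaired Q1 + 0.5·Q2.
- At midpoint, stopping at the last midpoint: normal 0.75·P1 + P2 + P3 + 1.25·P4 + 0.375·P5; impaired 0.75·Q1 + 0.5·Q2.
- At midpoint, last value carried to 12 h: add 0.5·P5 and 0.5·Q2 to the previous line.
- Concentration × interval length: the shares sum to 100 on both grids.

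**One case in full (half-life 1.74 h).** P = 31.45, 38.34, 17.30, 7.81, 5.11; Q = 87.08, 12.92.
- Interval end: 101.36 against 93.54; 93.54/101.36 = 0.923, or −7.7%.
- Midpoint, stopped: 90.91 against 71.77; ratio 0.79, or −21%.
- Midpoint, carried: 93.46 against 78.23; ratio 0.837, or −16.3%.

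**AUC(0-12), impaired grid relative to normal grid, same curve:**

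| CL, V (half-life) | Interval end | Midpoint, carried to 12 h | Midpoint, stopped |
|---|---|---|---|
| 42.9, 82.6 (1.34 h) | −5.0% | −16.0% | −19.0% |
| 43, 91 (1.47 h) | −5.9% | −16.2% | −19.8% |
| 26.0, 65.2 (1.74 h) | −7.7% | −16.3% | −21.0% |
| 29, 91 (2.18 h) | −10.0% | −16.1% | −22.3% |
| 29, 150 (3.59 h) | −14.1% | −14.7% | −23.9% |

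Half-lives up to 12 h and three two-compartment curves stay within about 5-24%, always lower on the impaired grid.

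**Later horizons, the five cases above.** AUC(0-24): −1.2% to −6.2% at interval end, −12.3% to −15.1% at midpoint. AUC(0-48): −1.2% to −5.8% and −12.2% to −15.0%.

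**Does a common grid cure it?** With the same curve shape, yes. With different shapes, the interval-end trapezoid on 0-6 and 6-12 h returns 95.4% of the true AUC(0-12) at CL 43, V 91; 90.9% at CL 29, V 91; and 85.1% at CL 29, V 150. The ratios 90.9/95.4 = 0.953 and 85.1/95.4 = 0.892 leave a spurious group difference of about 5-11%.

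**The case against.** Much of the other side stands.
- **The size is conditional.** It rests on an assumed half-life, constant urine flow and a time convention the SAP leaves open. The 19-24% end arises only if the midpoint curve stops at the last midpoint, 10 h in normal and 9 h in impaired subjects, which is not the 0-12 h area Table 5 defines.
- **The consequence is limited.** The listed ANOVA and regression tables cover plasma parameters only, and Table 3.7 is descriptive. SAP Table 3 does tick a statistical analysis for urine parameters, but no urine model or table follows. Ae total and fe% already describe urinary excretion without a trapezoid.

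Two stronger readings are tempting, and the documents do not support them.
- A reader might infer that a primary endpoint is affected, because SAP 2.2 also states "Urine primary PK end points include Ae total, AUC(t0-t1), fe%, and CLr of gepotidacin, as data permit". But AUC(t0-t1) is defined only as the predialyzer partial area during dialysis. The SAP synopsis and the protocol give the urine primaries as Ae total, fe% and CLr. The entry looks misplaced and needs its own correction.
- A reader might set the artefact against the confidence-interval half-widths of 21.77% to 23.00%. Those are for plasma Cmax and AUC; no precision is given for urine AUC.

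What does not stand is the idea that this is only missing detail. Every time convention tried with the stated trapezoid reads low on the impaired grid, so stating a convention alone would not remove the difference.

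**Conclusion.** The point holds for the secondary urine AUC and its descriptive normal-versus-impaired summary. Under a 2-h infusion, one compartment (CL about 26-43 L/h, V about 65-150 L), constant urine flow and zero predose concentration, identical excretion yields an AUC(0-12) about 5-24% lower on the impaired grid: 5-14% at interval end, 15-16% at midpoint carried to 12 h, 19-24% at midpoint stopped early. For AUC(0-24) and AUC(0-48) it is about 1-15%. The direction was the same in every case; the percentage is not a property of the documents and should be quoted only with its assumptions.

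Plasma parameters, Ae total and fe% are untouched. CLr is untouched provided its denominator is plasma AUC(0-t). The protocol's parameter list implies this, but SAP Table 5 puts the label AUC(0-t) on the urine area and then uses the same label in the CLr formula.

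**What to change.** In SAP Table 5, replace the trapezoid with the sum of interval concentration × interval length for all groups. At constant flow this gives 0% artefact on either grid and makes the time convention unnecessary.

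If the trapezoid is kept, at least pool the normal-subject collections, volume-weighted, to 0-6 and 6-12 h, and state the time assigned to each concentration and how the curve reaches 12, 24 and 48 h. This removes the grid difference but not the shape-dependent trapezoid error. Dropping urine AUC is the third option.

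In the same revision:
- reconcile the AUC(t0-t1) entry among the urine primary endpoints in SAP 2.2 with the SAP synopsis and the protocol;
- write CLr as Ae total divided by plasma AUC(0-t);
- record urine AUC in SAP 2.1 as an addition to the protocol, if it is kept.

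The cost is a few lines of derivation text. Concentrations and interval lengths are already needed for the planned AUC, and pooling needs only the urine volumes already required for Ae. No sampling or visit changes.

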**NOTES:**

- Additional parameters may be included as required.

**Table 6 Derived Dialysate Pharmacokinetic Parameters**

Parameter	Parameter Description
Arem(0-1)	Amount of drug removed by hemodialysis from time 0 to 1 hours after the start of hemodialysis
Arem(1-2)	Amount of drug removed by hemodialysis from time 1 to 2 hours after the start of hemodialysis
Arem(2-3)	Amount of drug removed by hemodialysis from time 2 to 3 hours after the start of hemodialysis
Arem(3-4)	Amount of drug removed by hemodialysis from time 3 to 4 hours after the start of hemodialysis (or to the end of dialysis if less than 4 hours)
Arem(0-4)	Cumulative amount of drug removed by hemodialysis from time 0 to 4 hours after the start of hemodialysis (or to the end of dialysis if less than 4 hours)
AUC(t0-t1)	Partial area under the curve estimated from predialyzer samples collected from start of dialysis (t0) to end of dialysis (t1)
CLD	Dialysis clearance, calculated as the total amount of the analyte recovered in the dialysate over 4 hours (or the total dialysis interval if less than 4 hours) divided by the partial area under the curve during the period of dialysis, which will be calculated using the predialyzer samples
Frem%(0-4)	Fraction (%) of the dose removed by hemodialysis from 0 to 4 hours after the start of hemodialysis (or to the end of dialysis if less than 4 hours)

**NOTES:**

- Additional parameters may be included as required.

**Table 7 Derived Saliva Pharmacokinetic Parameters (subjects in Part 1 only)**

Parameter	Parameter Description
AUC(0-t)	Area under the concentration-time curve from time 0 (predose) to time of last quantifiable concentration, to be calculated using the linear trapezoidal rule for each incremental trapezoid and the log trapezoidal rule for each decremental trapezoid.
AUC(0-∞)	Area under the concentration-time curve from time 0 (predose) extrapolated to infinite time, calculated as: $AUC = AUC(0-t) + C(t) / \lambda z$
%AUCex	The percentage of AUC (0-∞) obtained by extrapolation (%AUCex) will be calculated as: $[AUC(0-inf) - AUC(0-t)] / AUC(0-inf) \times 100$
Cmax	Maximum observed concentration, determined directly from the concentration-time data.
Tmax	Time to first occurrence of Cmax
t1/2	Terminal phase half-life will be calculated as: $t_{1/2} = \ln 2 / \lambda z$
λz	Terminal-phase rate constant
CL	Systemic clearance, calculated as: $CL = \text{Dose} / AUC(0-inf)$
Vss	Volume of distribution at steady-state of parent drug, calculated as: $V_{ss} = MRT(0-inf) * (CL)$
Vz	Volume of distribution of the terminal phase, calculated as: $V_z = \text{Dose} / (AUC(0-inf) * \lambda z)$
RAUC(0-t)	The ratio of the AUC(0-t) observed in saliva relative to the AUC(0-t) in plasma, calculated as: $RAUC(0-t) = AUC(0-t) \text{ saliva} / AUC(0-t) \text{ plasma}$
RAUC(0-∞)	The ratio of the AUC(0-∞) observed in saliva relative to the AUC(0-∞) in plasma, calculated as: $RAUC(0-\infty) = AUC(0-\infty) \text{ saliva} / AUC(0-\infty) \text{ plasma}$

**NOTES:**

- Additional parameters may be included as required.

### 7.1.3.2. Statistical Analysis of Pharmacokinetic Parameters

The following pharmacokinetic statistical analyses will only be performed, if sufficient data is available (i.e. if subjects have well defined plasma profiles).

Pharmacokinetic Statistical Analyses
Endpoint(s)

 
Plasma primary pharmacokinetic (PK) endpoints include AUC(0-∞), AUC(0-t) and Cmax of gepotidacin, as data permit
 

Model Specification

 
The log-transformed AUC(0-∞), AUC(0-t), and Cmax values for gepotidacin in the renal impairment groups and normal renal function groups will be compared using an analysis of variance.
 
Linear regression analysis will be used to evaluate the relationships between estimated renal function and relevant PK parameters (e.g., AUC, Cmax, and CL).
 
An exploratory analysis will be performed to explore the relationship between saliva and plasma concentrations and PK parameters.
 

Model Checking & Diagnostics

 
Refer to Appendix 9: Model Checking and Diagnostics for Statistical Analyses.
 

Model Results Presentation

 
Statistical analysis by ANOVA will be presented in tabular format with geometric mean ratios between renal impairment groups and normal renal function groups, and 90% CIs for the ratios of AUC(0-∞) and Cmax for gepotidacin. Example SAS Code:   <pre>PROC MIXED; CLASS GRPID; MODEL LOGPKPARAM = GPRID/DDFM=KR; LSMEANS GRPID; ESTIMATE 'B VS A' GPRID -1 1 0/CL ALPHA=0.1; ESTIMATE 'C VS A' GPRID -1 0 1/CL ALPHA=0.1;RUN;</pre> 
 
Statistical analysis by linear regression will be presented in tabular format if the data permits with identification of linear functions that fit the data well, the resulting slopes will provide a comparison of any difference in the response of the gepotidacin IV treatment as renal function changes. Example SAS Code:   <pre>PROC MIXED; MODEL LOGPKPARAM = RENAL_FUNCTION/S DDFM=KR; ODS OUTPUT SOLUTIONF=S; RUN;</pre> 
 
Statistical analysis by linear regression will be presented in graphical format with scatter plots of PK parameters by eGFR and PK parameters by Clcr with identification of linear functions
 

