3. OBJECTIVES AND ENDPOINTS

Objectives	Endpoints
Primary	

 To compare the pharmacokinetics of gepotidacin administered as a 750-mg IV dose in normal healthy subjects compared with subjects with mild, moderate, and severe renal impairment, and with subjects with end-stage renal disease (ESRD) 	
 Plasma primary pharmacokinetic (PK) endpoints include AUC(0-∞) and Cmax of gepotidacin, as data permit Urine primary PK end points include Ae total, fe%, and CLr of gepotidacin, as data permit Dialysate primary PK end points include AUC(t0-t1), CLD, and Frem%(0-4), of gepotidacin, as data permit
Secondary	

 To assess the safety and tolerability of gepotidacin administered as a 750-mg IV dose in normal healthy subjects compared with subjects with mild, moderate, severe renal impairment, and with subjects with ESRD 	
 12-lead safety electrocardiogram readings, change from baseline in vital sign measurements (blood pressure and heart rate), monitoring of adverse events, toxicity grading of clinical laboratory test results, and physical examinations

 To evaluate the secondary PK parameters of gepotidacin administered as a 750-mg IV dose in normal healthy subjects compared with subjects with mild, moderate, and severe renal impairment, and with subjects with ESRD 	
 Plasma PK endpoints include AUC(0-t), CL, λz, t1/2, Tmax, Vss, and Vz, as data permit Urine PK endpoint includes Ae(t1-t2), as data permit Dialysate PK endpoints include Arem(0-1), Arem(1-2), Arem(2-3), Arem(3-4), and Arem(0-4), as data permit
Exploratory	

 To evaluate the saliva pharmacokinetics of gepotidacin (subjects in Part 1 only) 	
 Primary PK endpoints include AUC(0-∞) and Cmax of gepotidacin, as data permit Secondary PK endpoints include AUC(0-t), CL, λz, t1/2, Tmax, Vss, and Vz, as data permit

ESRD = end-stage renal disease; PK = pharmacokinetic

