**Table 3 Overview of Planned Pharmacokinetic Analyses**

Display Type	Untransformed							Log-Transformed						
	Stats Analysis			Summary		Individual		Stats Analysis			Summary		Individual	
	T	F	L	T	F	F	L	T	F	L	T	F	F	L
PK Concentrations				Y	Y  [2]	Y 	Y				Y	Y	Y	
Plasma PK Parameters	Y			Y	Y	Y	Y	Y	Y	Y	Y	Y		
Urine PK Parameters	Y			Y	Y	Y	Y	Y	Y	Y	Y	Y		
Saliva PK Parameters	Y			Y	Y	Y	Y	Y	Y	Y	Y	Y		
Dialysate PK Parameters 	Y			Y	Y	Y	Y	Y	Y	Y	Y	Y		

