## 9.11.7. Pharmacokinetic Figures

Pharmacokinetic : Figures					
No.	Population	IDSL / TST ID / Example Shell	Title	Programming Notes	Deliverable [Priority]
Concentration Plots					
3.1	PK	PKCF4	Mean Gepotidacin Plasma Concentrations by Renal Function (Linear and Semi-Log)	Dashed line represents the LLQ. Present all treatment groups in the same plots.	SAC [1]
3.2	PK	PKCF4	Mean Gepotidacin Urine Concentrations by Renal Function (Linear and Semi-Log)	Dashed line represents the LLQ. Present all treatment groups in the same plots. Plot concentration at the collection midpoint.	SAC [1]
3.3	PK	PKCF4	Mean Gepotidacin Saliva Concentrations by Renal Function (Linear and Semi-Log)	Dashed line represents the LLQ. Present all treatment groups in the same plots.	SAC [1]
3.4	PK	PKCF1P	Individual Gepotidacin Plasma Concentrations by Renal Function (Linear and Semi-Log)	Dashed line represents the LLQ. Present all treatment groups in the same plots.	SAC [1]
3.5	PK	PKCF1P	Individual Gepotidacin Urine Concentrations by Renal Function (Linear and Semi-Log)	Dashed line represents the LLQ. Present all treatment groups in the same plots. Plot concentration at the collection midpoint.	SAC [1]
3.6	PK	PKCF1P	Individual Gepotidacin Saliva Concentrations by Renal Function (Linear and Semi-Log)	Dashed line represents the LLQ. Present all treatment groups in the same plots.	SAC [1]

Pharmacokinetic : Figures					
No.	Population	IDSL / TST ID / Example Shell	Title	Programming Notes	Deliverable [Priority]
Parameter Plots					
3.6	PK Parameters	PK_F1	Scatter Plot to Explore the Relationship between Gepotidacin Plasma Pharmacokinetic Parameters by Renal Function	Present all treatment groups in the same plots. Repeat for CrCL. Repeat for parameter AUC(0-t) and CL	SAC [1]
3.7	PK Parameters	PK_F2	Scatter Plot to Explore the Relationship between Gepotidacin Urine Pharmacokinetic Parameters by Renal Function	Present all treatment groups in the same plots. Repeat for CrCL.	SAC [1]
3.8	PK Parameters	PK_F3	Scatter Plot to Explore the Relationship between Gepotidacin Saliva Pharmacokinetic Parameters by Renal Function	Present all treatment groups in the same plots. Repeat for CrCL. Repeat for parameter AUC(0-t) and CL	SAC [1]
Exploratory Objectives					
3.9	PK	PK_F4	Scatter Plot of Gepotidacin Saliva and Plasma Concentrations by Renal Function	Present all treatment groups in the same plots.	SAC [1]

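### The primary urine endpoints (CLr, fe%, Ae total) have no planned between-group ratio with CI and no tabulated regression slope, although SAP Table 3 marks formal analysis for urine

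*SAP*

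**What the plan says.** Protocol section 3 opens the primary objective with "To compare the pharmacokinetics of gepotidacin administered as a 750-mg IV dose in normal healthy subjects compared with subjects with mild, moderate, and severe renal"; the sentence then extends to ESRD. Among the endpoints under that objective: "Urine primary PK end points include Ae total, fe%, and CLr of gepotidacin, as data permit". SAP section 2.2 gives a slightly different list: "Urine primary PK end points include Ae total, AUC(t0-t1), fe%, and CLr of gepotidacin, as data permit". Protocol 9.1 and SAP 2.4 rule out formal hypothesis testing and commit to estimation against matched normal subjects.

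The modelling text is narrower. The endpoint line of SAP 7.1.3.2 reads "Plasma primary pharmacokinetic (PK) endpoints include AUC(0-∞), AUC(0-t) and Cmax of gepotidacin, as data permit". The ANOVA output there is "Statistical analysis by ANOVA will be presented in tabular format with geometric mean ratios between renal impairment groups and normal renal function groups", with "90% CIs for the ratios of AUC(0-∞) and Cmax for gepotidacin". Protocol 9.4.1 has the same scope, and SAP Appendix 9 lists only the two AUCs and Cmax.

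In SAP Table 3, the row "Urine PK Parameters" is marked under the statistical-analysis columns, which the table's notes define as formal modelling. In Appendix 11, Table 3.10 (ANOVA) and Table 3.11 (regression) are both titled for plasma. Urine has a summary (Table 3.7) and a figure titled "Scatter Plot to Explore the Relationship between Gepotidacin Urine Pharmacokinetic Parameters by Renal Function", repeated for creatinine clearance.

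**The concern.** A comparative primary objective under an estimation approach needs, for each primary endpoint, either a named contrast with its precision or a statement that the endpoint is descriptive. The urine endpoints have neither, and two parts of the SAP disagree on whether they are to be modelled.

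CLr is the parameter tied most directly to the question. Protocol 2.1 rests the study on renal clearance being about 40% of total clearance. The simulations in protocol 4.5 changed only GFR and assumed no active renal secretion, because renal uptake was poorly understood. CLr by group and against eGFR is the study's direct check on that assumption. The plasma AUC ratio is only an indirect one, since it mixes renal and nonrenal change.

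**Working it through.** **1. What is specified for each type of output**

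| Output | Plasma AUC, Cmax | CLr, fe%, Ae total |
|---|---|---|
| Marked as formal analysis in SAP Table 3 | Yes | Yes |
| Named for the ANOVA in SAP 7.1.3.2 | Yes | No |
| Between-group ratio with 90% CI | AUC(0-∞) and Cmax | None |
| Model table in Appendix 11 | 3.10, 3.11 | None |
| Within-group summary | Table 3.6 | Table 3.7 |
| Plot against eGFR and Clcr | Yes | Figure 3.7 |

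The urine marks in Table 3 have no model or model table behind them.

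**2. The plan's own precision figure**

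Protocol 9.2.1 gives CVs of 26.3%, 27.4% and 27.6% (Cmax, AUC(0-∞), AUC(0-t)), 16 versus 8 subjects, and 90% half-widths of 21.77%, 22.75% and 23.00%. Take the half-width as exp(t × SD × sqrt(1/16 + 1/8)) − 1, with t = t(0.95, 22 df):

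- SD = CV: 21.60%, 22.60%, 22.78%.
- SD = sqrt(ln(1 + CV²)): 21.20%, 22.15%, 22.32%.

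Neither matches to two decimals, but both are within 3% (relative) of the stated values, so the formula is suitable here.

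**3. The same formula for a CLr ratio**

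The documents give no CV for any urine parameter, so the CV is assumed and shown over a range. The Part 1 model has three groups (16, 8, 8), so the error df are 32 − 3 = 29 and t = 1.699. Also sqrt(1/16 + 1/8) = 0.433.

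- CV 20%: SD 0.198; exp(1.699 × 0.198 × 0.433) − 1 = 16%.
- CV 30%: SD 0.294; half-width 24.1%.
- CV 50%: SD 0.472; half-width 41.6%.
- CV 80%: SD 0.703; half-width 68%.

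These are the upper sides. The lower limits are the estimate times 0.864, 0.806, 0.706 and 0.596.

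Part 2 is smaller. With 4 versus 4 (the low end of protocol 4.3; 6 df) the factor either side is 1.70 at CV 40%. With 8 versus 8 (14 df) it is 1.40.

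**4. Whether the plasma ratio can stand in**

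Protocol Appendix 11 gives total clearance 43 L/h and renal clearance 16 L/h, so nonrenal clearance is 43 − 16 = 27 L/h. Losing all renal clearance with no other change would raise AUC by 43/27 = 1.59.

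For illustration, take an observed AUC ratio of 1.6 with the factor 1.22 that follows from CV 27.4%. The interval is 1.6/1.22 = 1.31 to 1.6 × 1.22 = 1.95.

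- Lower limit: 43/1.31 = 32.8 L/h, a loss of 10.2 L/h, or 10.2/16 = 64% of renal clearance and no nonrenal change.
- Upper limit: 43/1.95 = 22.0 L/h, which is all renal clearance lost plus 27 − 22.0 = 5 L/h of nonrenal clearance.

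So the AUC interval is compatible with partial renal loss, full renal loss, or full renal loss with a nonrenal change as well.

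**5. The CLr denominator**

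SAP Table 5 defines AUC(0-t) as an area under urine concentrations, then divides Ae total by AUC(0-t) to obtain CLr. In protocol 9.4.1 the only AUC(0-t) defined ahead of CLr is the plasma one. Read literally, the SAP table gives a different quantity.

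**The case against.** The case for leaving the plan alone has substance. The stated rationale is whether renal function alters plasma pharmacokinetics, and the plasma contrasts that serve it are specified. Nothing is tested, and the urine endpoints apply as data permit. Protocol 9.4.1 itself plans only listings and summary statistics for urine, and the SAP follows it. All four parameter rows of Table 3 carry the same marks, so the urine marks may be template fill. On that view the defect is an inconsistency, which an explicit statement that urine is descriptive would also cure. That stands, and the fix keeps it as an alternative.

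Two stronger readings are tempting, and the documents do not support them.

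- A reader might infer that urine gets no regression at all. The regression list in SAP 7.1.3.2 is open (AUC, Cmax and CL are examples), its graphical regression is not limited to plasma, and Figure 3.7 applies it to urine. What is missing is a tabulated slope with an interval.
- A reader might infer that the effect on renal clearance is never estimated. Table 3.7 summarises CLr, fe% and Ae total. SAP 9.3.3 provides geometric means with 95% CIs for log-transformed parameters, and these three are not on its list of exceptions. Group levels can be read off; the contrast and its precision are what is absent.

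The precision argument also has limits. The urine CV is unknown, and 29 df needs full enrolment and a common variance, while protocol 4.3 says up to 16 normal subjects. The documents predict no size for the fall in CLr; 16 L/h is only a model input.

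**Conclusion.** The point holds in this form: following the SAP yields no between-group ratio with CI and no tabulated slope for any primary urine endpoint, despite a comparative objective and despite Table 3. It concerns specification and internal consistency. It does not threaten the plasma conclusions.

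The planned Part 1 numbers would support a CLr ratio with a 90% half-width of about 24% at CV 30% and 42% at CV 50%. Those CVs are assumptions, and the calculation assumes 16, 8 and 8 evaluable subjects with a pooled variance. Part 2 intervals would be wider. The AUC illustration assumes the clearances in protocol Appendix 11 and shows only that the plasma ratio does not replace a CLr contrast.

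**What to change.** - **ANOVA (SAP 7.1.3.2, with a urine counterpart to Table 3.10).** Add log CLr and log fe%, as geometric mean ratios with 90% CIs: B and C versus A in Part 1, and E versus normal in Part 2 if E is enrolled, naming the normal group used if D is not. At a common 750-mg dose the fe% ratio is also the Ae total ratio, because fe% is Ae total divided by a constant, so one row serves both. Say so in a footnote.
- **Regression (Table 3.11).** Add CLr on eGFR, and on Clcr where Clcr is available, with slope and CI. State the scale.
- **No measurable urinary drug.** Restrict these models to subjects with measurable urinary drug and report by group how many have none. This matters for Group C, which includes ESRD not on hemodialysis: leaving out such subjects would understate the fall in that group. Keep Group F urine descriptive.
- **SAP Table 5.** State that the CLr denominator is plasma AUC(0-t) over the urine collection period.
- **Endpoint list.** Reconcile the urine endpoints in SAP 2.2 with the protocol, since AUC(t0-t1) is defined only for dialysis.

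If the sponsor prefers not to model urine, the alternative is to state that these endpoints are descriptive only and remove the urine marks under statistical analysis in Table 3.

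The cost is small: no new data, and example code already written for a generic log parameter, though E versus normal needs its own contrast. The downside is a few more table rows and intervals that may be wide.
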